	
the patient for TAVI in their hospital without on-site surgery.
 
CONTROL ARM: TAVI WITH ON-SITE SURGERY
 
After randomization, the patient will immediately be placed on the waiting list of the referring center with on-site cardiac surgery. Study TAVI operators of the participating center will perform the TAVI procedure in the hospital with on-site surgery according to the waiting list schedule of the latter.

Number of participants	566
Trial Location	Approximately 20 Italian centers without on-site cardiac surgery
Requirements for participating centers	
 
1. Availability of standard operating procedure with a cardiac surgery department for an established, weekly Heart Team discussion
 
2. Availability of standard operating procedure for the rapid transfer of patients with procedural complications to cardiac surgery with a maximum delay of 60 minutes (maximum distance between centers 90 km)
 
3. Five-year experience in screening, selection, and management of TAVI patients
 
4. At least 2 certified operators or a dedicated intercenter team performing the TAVI procedure (see detailed criteria list)
 
5. At least 3-year experience in performing TAVI procedures in a center with on-site cardiac surgery, with participation (as equipe) in at least 100 TAVI procedures
 
6. At least 5-year experience in advanced cardiac imaging including transoesophageal echocardiography and cardiac computed tomography
 
7. On-site vascular surgery or on-site availability of certified surgeon and operating room allowing the surgical treatment of vascular complications
 
8. On-site electrophysiology laboratory (permanent pacemaker implantation)
 

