## 5.5 Randomization

Randomization will be performed after the signature of the informed consent. Randomization will be performed centrally using an internet-based system. The patient identification number (Patient ID) and the treatment allocation will be assigned by the central randomization system. Treatment allocation will be assigned according to a computer-generated randomization list stratified by center. Randomization will also be stratified by sex, surgical risk (inoperable vs. other), age (<85 vs. ≥85 years) and valve (self-expandable vs. balloon-expandable). Patients will be randomized to the following:

- EXPERIMENTAL ARM: TAVI WITHOUT ON-SITE SURGERY
- CONTROL ARM: TAVI WITH ON-SITE CARDIAC SURGERY

All patients who are randomized are irrevocably in the study, whether or not they are subsequently found to be eligible, or actually receiving the allocated treatment. Therefore, all patients must be followed until the prespecified study end date.

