A detailed statistical analysis plan will be completed before the end of the study. In summary, continuous variables will be tested for normal distribution with the Kolmogorov-Smirnov test and with visual estimate of the QQ plot. Normally distributed variables will be presented as mean±SD and compared using the t test and one-way ANOVA. Otherwise, the median [inter-quartile range], Mann-Whitney U and Kruskal-Wallis tests will be used. Categorical variables will be summarized in terms of absolute and relative frequencies (percentages) and compared using  $\chi^2$  test. Statistical significance will be established at  $\alpha=0.05$  level. Formal type-I error control will be ensured for the primary and the secondary endpoint by correction for multiple testing according to Holm, and Bretz graphical approaches. Kaplan-Meier curves will be plotted to describe survival free from adverse events, and difference between groups will be tested with log-rank test. Further analyses will be performed setting as landmark the timing of TAVI procedure. Any confounding factor will be tested by Cox regression models. Variables with a p-value <0.1 in univariate analysis will be entered in a multivariate analysis to identify independent predictors. When appropriate, 95% CI will be calculated. In addition to the analysis of the first event, we will assess the primary composite outcome using the Finkelstein-Schoenfeld method, which is based on the principle that each patient in the clinical trial is compared with every other patient in a pairwise manner. The pairwise comparison proceeds in a hierarchical fashion, using all-cause mortality, followed by the frequency of hospital readmission when patients cannot be differentiated on the basis of mortality. This method gives a greater importance to all-cause mortality. We will apply the Finkelstein–Schoenfeld and the win ratio methods (Pocock et al, Eur Heart J 2012) to the patients stratified according to sex (male vs. female) and surgical risk (inoperable vs. other), yielding four stratification pools.

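### The stated tests and Cox screening rule (univariate p<0.1) do not carry the five randomization factors into the treatment comparison; fix a short adjustment set instead

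*Protocol*

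**What the plan says.** **Allocation (Protocol 5.5).** "Treatment allocation will be assigned according to a computer-generated randomization list stratified by center". The next sentence adds four binary factors: "Randomization will also be stratified by sex, surgical risk (inoperable vs. other), age (<85 vs. ≥85 years) and valve (self-expandable vs. balloon-expandable"). The synopsis expects "Approximately 20 Italian centers without on-site cardiac surgery" and 566 patients.

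**Analysis (Protocol 9).**
- Categorical variables are compared by chi-square. For the Kaplan-Meier curves, "difference between groups will be tested with log-rank test". Neither sentence mentions strata, and neither test is named as the non-inferiority test.
- "Any confounding factor will be tested by Cox regression models". The next sentence gives the entry rule: "Variables with a p-value <0.1 in univariate analysis will be entered in a multivariate analysis to identify independent predictors". No list of candidate variables is given.
- The Finkelstein-Schoenfeld and win-ratio analyses of the primary composite are "stratified according to sex (male vs. female) and surgical risk (inoperable vs. other), yielding four stratification pools". Center, age and valve are not used there.
- The section is a summary. A detailed SAP is to be completed before the end of the study.

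**The concern.** When randomization is stratified on prognostic factors, an analysis that ignores them reports a standard error larger than the true spread of the estimate. The test stays valid but gives away some precision. Analyzing by the factors used in randomization recovers it and fixes the adjustment set before any outcome is seen.

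The protocol instead writes in a rule driven by outcome data. Such a screen can drop a design factor that happens to miss p<0.1 and admit another by chance, and intervals from the selected model take no account of the selection. Nothing restricts it to baseline variables. Two post-randomization quantities are within reach. One is the valve actually received, which section 5.6 says may differ from the one declared. The other is time on the waiting list, which depends on the allocated arm (sections 7.1 and 7.2) and is a secondary endpoint (section 4.2). Adjusting for waiting time would remove part of the pathway effect under test. The protocol does not say that either variable will be used, but the rule does not exclude them.

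**Working it through.** **1. The plan's own figure.** Inputs from section 9.1 and the synopsis: 30% event rate (taken as equal in both arms), absolute margin 10 points, 2:1 allocation, alpha 5% (sidedness not stated), power 80%, 1% attrition.
- Farrington-Manning (score) formula at one-sided 5%: 185.8 controls, so 186 + 372 = 558, against the stated 187 + 373 = 560.
- Unpooled variance at one-sided 5%: (1.645 + 0.842)² × 0.21 × 1.5 / 0.10² = 194.8 controls, so 195 + 390 = 585.
- Attrition: 560 / 0.99 = 565.7, i.e. 566.

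The stated size therefore reproduces to within 2 patients with an unstratified score-type calculation at one-sided 5%. It does not rely on any gain from adjustment.

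**2. How fine the strata are.** If all five factors are fully crossed: 20 × 2 × 2 × 2 × 2 = 320 cells, and 566 / 320 = 1.77 patients per cell. With patients spread evenly (assumption; Poisson, mean 1.77), about 17% of cells are empty and about 74% hold fewer than 3 patients. A log-rank test stratified on all cells would therefore not be workable; adjustment has to go through a small number of main effects.

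**3. What ignoring the factors costs: simulation.** Assumptions: 566 patients, 20 centers of equal expected size, each binary factor split evenly, permuted blocks of 3 within each cell, one-sided 5%, 2,000 runs per setting. The adjusted analysis is a linear model with the four factors and 19 center indicators, with robust standard errors.

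| Assumed effects on 1-year risk | Type I error, unadjusted / adjusted | Power, unadjusted / adjusted |
|---|---|---|
| None | 4.4% / 4.6% | 80.7% / 80.3% |
| Center SD 5 points; factors 5, 10, 10, 0 points | 5.5% / 5.2% | 79.8% / 80.5% |
| Center SD 8 points; factors 5, 15, 15, 5 points | 4.2% / 4.6% | 78.5% / 80.3% |

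Simulation error is about ±1 point on type I error and ±2 points on power. In the strongest setting (power runs), the unadjusted standard error averages 0.0408 while the estimate's actual SD is 0.0396. The adjusted standard error averages 0.0393 against an SD of 0.0394. Adjustment mainly corrects the reported standard error.

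**4. Closed-form ceiling.** The unadjusted SE is √(0.21/187 + 0.21/373) = 0.0411, so power = Φ(0.10/0.0411 − 1.645) = 78.5%. If the factors explain a share R² of outcome variance, the SE shrinks by √(1 − R²):
- R² = 5%: SE 0.0400, power 80.3%.
- R² = 10%: SE 0.0390, power 82.2%.

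This treats the covariates as free. The strongest simulated setting has R² = (0.08² + (0.05² + 0.15² + 0.15² + 0.05²)/4) / 0.21 = 9.0%, and it gained only about 2 points once 23 covariates were estimated. The gain of nearly 4 points at R² = 10% is thus an upper bound.

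**The case against.** The strongest reply is that choosing covariates and strata is ordinary SAP content. Section 9 is explicitly a summary, and the log-rank sentence does not exclude strata. That stands for the missing strata taken alone. It does not cover the p<0.1 rule, which the protocol states outright and which a consistent SAP would inherit.

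A second reply is that the rule's declared aim is to find independent predictors, which is prognostic modeling, and that no sentence makes it the source of the non-inferiority estimate. That is right. But it directly follows the sentence on confounding, and in a two-arm trial a model for confounding readily reads as an adjusted treatment effect. The text leaves both readings open.

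A reader might infer several stronger things that the protocol does not support:
- *That the adjusted estimate could move across the margin.* The margin in section 9.1 is an absolute 10-point difference. The screened model is a Cox model giving a hazard ratio, for which no margin is set.
- *That the whole analysis is unstratified.* The win-ratio analysis is stratified by sex and surgical risk. Using two factors there is a defensible choice, since more pools leave fewer within-pool pairs.
- *That stratification will fail to balance the factors, so allocation must be redesigned.* Small cells are a fact only if the factors are fully crossed. Section 5.5 gives no block size or algorithm, and sparse cells alone do not measure balance on each factor. For valve type, section 5.6 adds separate monitoring and correction.
- *That type I error is inflated.* The simulations show no sign of it.

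**Conclusion.** The concern holds in a limited form. Randomization uses five factors. The stated between-group tests name none of them, the win ratio uses two, and the Cox text carries a data-driven entry rule that protects neither the design factors nor the restriction to baseline variables.

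The unadjusted randomized comparison is not biased. The loss is about 0 to 2 points of power at one-sided 5%, resting on assumed prognostic effects, even center sizes and blocks of 3, none of which the protocol gives. The second cost is not quantified: an adjusted treatment estimate, if one is reported from this rule, could depend on which variables pass the screen. The point is worth correcting because the remedy is specific and nearly free, not because the trial's conclusion is at risk.

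**What to change.** In section 9, and then in the SAP:
1. Pre-specify the primary 1-year risk difference as adjusted for sex, surgical risk, age group and the valve type declared at randomization, with center as a random effect or small centers pooled. Use the same set in any Cox model that reports a treatment effect. The unadjusted result can be shown beside it.
2. State that the p<0.1 entry rule applies only to exploratory modeling of predictors.
3. State that no variable arising after randomization, such as the valve received or waiting time, enters a treatment-effect model.

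No change to the allocation system, the win-ratio strata or the sample size is needed. The factors are already recorded at randomization, so no new data are required. The cost is a few sentences and a slightly more complex primary model, whose form and handling of small centers should be fixed before outcome data by arm are seen.

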### 9.1 Determination of sample size

The occurrence of the primary endpoint will be computed from the randomization. Therefore, adverse events occurring between randomization and TAVI procedure will be considered. The primary endpoint is the 1-year occurrence of all-cause death and hospital readmission for cardiovascular cause. The estimated rate of the primary endpoint is around 30%, considering the characteristics of the study population and the inclusion of adverse events before TAVI [1-29]. Overall, 560 (187 control arm and 373 experimental arm)

patients are required to exclude a difference in favor of the control group of more than 10% ( $\alpha=5\%$  and  $\beta=20\%$ ). Considering a 1% attrition rate final sample size is inflated to 566 patients.

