## 1 STUDY SYNOPSIS

Study Title	Transcatheter Aortic Valve Implantation with or without on-site Cardiac Surgery: the TRACS trial
Protocol version	V2
Date	February 20, 2024
Study Sponsors	
Azienda USL di Bologna, Bologna, Italy
 
Azienda Ospedaliero Universitaria di Ferrara, Cona (FE), Italy
 
Azienda USL-IRCCS di Reggio Emilia, Reggio Emilia, Italy
 
The present trial received the endorsement of the Italian Health Minister that partially supported the conduction of the study with the grant GR-2021-12374295 (Ricerca Finalizzata 2021)

Study Principal Investigator	[name]
Study Chairs	
[name]
 
[name]

Study Objectives	
The primary efficacy objective is to determine whether a TAVI pathway based on experienced operators who perform the procedure in the center without on-site cardiac surgery is non inferior compared to the one with the same team who perform the procedure in the center with on-site cardiac surgery in terms of all-cause death, stroke and rehospitalization for cardiovascular cause..
 
The primary safety objective is to demonstrate that mortality associated with periprocedural complications actionable by emergent cardiac surgery did not differ between study arms.

Study design	
TRACS is an all-comer, prospective, randomized, multicenter, open-label trial with blinded adjudicated evaluation of outcomes (PROBE). The TRACS trial will involve centers without on-site cardiac surgery, but with experienced operators already performing TAVI at the referring center with on-site cardiac surgery. Thus, participating centers and their study TAVI operators must follow selective criteria for eligibility. Participants will be recruited after Heart Team indication to TAVI procedure. The eligibility of each single patient to the study MUST BE CONFIRMED and VALIDATED by unanimous decision of the Heart Team. Study patients will be randomized in a 2:1 fashion to TAVI procedure performed by the same experienced operators either in the center without on-site cardiac surgery or in the referring center with on-site cardiac surgery.

Study arms	
EXPERIMENTAL ARM: TAVI WITHOUT ON-SITE SURGERY
 
After randomization, study TAVI operators of the participating center will schedule

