
Exclusion criteria
	
 
1. Unsuitable for transfemoral TAVI
 
2. Emergent TAVI
 
3. Noncardiovascular comorbidity reducing life expectancy to <1 year
 
4. Any factor precluding 1-year follow-up
 
5. Refusal informed consent
 

Primary endpoint
	
One-year cumulative occurrence of all-cause death, stroke and hospital readmission for cardiovascular causes
 
The adverse events will be collected from the time of randomization, also considering adverse events during the waiting time for the TAVI procedure.

Secondary efficacy endpoints
	
 
• All-cause death
 
• Cardiovascular death
 
• Myocardial infarction
 
• Hospital admission for cardiovascular cause
 
• Hospital admission for heart failure
 
• Cerebrovascular accident
 
• Ischemic stroke
 

	
 
• Hospital admission for pneumonia (<math>\pm</math> respiratory failure)
 
• Need for balloon aortic valvuloplasty for emergent condition
 
• Quality of life measured with the Eq-5D and KCCQ-12 scales
 
• Time spent on the waiting list before TAVI
 

Primary safety endpoint	Death due to periprocedural complications that can be addressed with emergent cardiac surgery
Other safety endpoints	
 
• Cardiac tamponade
 
• Bleeding
 
• Kidney failure (requirement of renal replacement therapy)
 
• Severe aortic regurgitation (aortic regurgitation according to current guidelines)
 
• Multiorgan failure (failure of at least two organ systems)
 
• Vascular access site and access related complications
 
• Conduction disturbances and arrhythmias
 
• Endocarditis
 
• Valve thrombosis
 
• Valve malpositioning
 
• Valve embolization
 
• Ectopic valve deployment
 
• TAV-in-TAV deployment
 

Assessment Schedule	Pre-eligibility screening, inclusion, randomization, TAVI, 1-month visit after TAVI, 6-month visit after TAVI, 12-month visit after TAVI, and every 12 months thereafter.
Study Duration	Enrollment will occur over approximately 2 years with an expected minimum follow-up of 12 months. All patients will be followed until 3 years.

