## 4 STUDY ENDPOINTS

### 4.1 Primary efficacy endpoint

- 1-year cumulative occurrence of all-cause death, stroke and hospital readmission for CV cause

To test if a TAVI pathway based on experienced operators who perform the procedure in the center without on-site cardiac surgery is non inferior compared to the one with the same team who perform the procedure in the center with on-site cardiac surgery.

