## 8.10 Clinical endpoints

Clinical adverse events of interest are defined in agreement with the consensus documents of the Valve Academic Research Consortium (VARC)-2 and VARC-3 and are described in the following [10, 30]. **It should be noted that the primary endpoint of the study has been selected in agreement with the suggestions of the VARC-3 consensus document that stated that the best composite endpoint of 1 year is that that combines all-cause mortality, stroke, and hospitalization for procedure or valve-related cardiovascular causes.**

---

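### Section 9.1 of the protocol defines the primary endpoint without stroke, contradicting the declared three-part composite, and the supplementary win-ratio hierarchy has no stroke tier

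*Protocol*

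**What the plan says.** Four places in the protocol include stroke:

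- Section 1, study objectives: non-inferiority "in terms of all-cause death, stroke and rehospitalization for cardiovascular cause".
- Section 1, primary endpoint row: "One-year cumulative occurrence of all-cause death, stroke and hospital readmission for cardiovascular causes".
- Section 4.1: "1-year cumulative occurrence of all-cause death, stroke and hospital readmission for CV cause".
- Section 8.10, which explains that the endpoint follows a consensus composite that "combines all-cause mortality, stroke, and hospitalization for procedure or valve-related cardiovascular causes".

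Two places do not:

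- Section 9.1: "The primary endpoint is the 1-year occurrence of all-cause death and hospital readmission for cardiovascular cause". The next sentence begins "The estimated rate of the primary endpoint is around 30" per cent, and the 560 patients (187 control, 373 experimental) follow from it.
- Section 9: "In addition to the analysis of the first event, we will assess the primary composite outcome using the Finkelstein-Schoenfeld method". The hierarchy is then described as "using all-cause mortality, followed by the frequency of hospital readmission when patients cannot be differentiated on the basis of mortality".

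The statistical row of the synopsis gives the same 30%, 187 + 373 = 560, and 566 after attrition. It stands in the same table as the endpoint that includes stroke.

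**The concern.** Section 9.1 does more than leave a detail to a later plan. It gives its own definition, which differs from the declared one. Section 9 says the detailed analysis plan will be completed before the end of the study, so its authors would inherit two definitions in an open-label trial where events are already accruing.

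Readmission does not fully stand in for stroke. Section 8.12 counts non-elective admissions after randomization, and its table leaves out stays planned for a pre-existing condition. A stroke during a scheduled TAVI stay that the patient survives is not a readmission. Without a stroke component, that event does not count unless the patient later has another qualifying event. It is also a procedural harm, in a trial that compares where the procedure is done. If such strokes were more frequent in the experimental arm, leaving them out would favour a conclusion of non-inferiority.

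**Working it through.** **Which events each wording counts** (from Sections 4.1, 8.12, 9 and 9.1)

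| Event | Declared endpoint (4.1) | Wording of 9.1 | Hierarchy in Section 9 |
|---|---|---|---|
| Fatal stroke | yes | yes, as death | yes, as death |
| Survived stroke leading to a qualifying admission | yes | yes, as readmission | yes, as readmission |
| Survived stroke during the scheduled TAVI stay | yes | no | no |

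The second row rests on Section 8.12, where stroke is among the listed causes of procedure-related or valve-related hospitalization.

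**Reproducing the stated sample size**

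Inputs from Section 9.1 and the synopsis: 30% (taken as equal in both arms), margin 10 points, alpha 5%, power 80%, allocation 2:1. The protocol does not say whether alpha is one-sided. One-sided 5% is assumed here because it matches the stated number.

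Farrington-Manning, with k = 2 experimental patients per control patient and x the control rate fitted under the null hypothesis of a 10-point excess:

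- v0 = x(1−x) + (x+0.10)(1−x−0.10)/k
- v1 = p(1−p)(1 + 1/k)
- n(control) = [(1.645√v0 + 0.842√v1)/0.10]²

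At p = 0.30, x = 0.2381:

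- v0 = 0.2381×0.7619 + 0.3381×0.6619/2 = 0.2933
- v1 = 0.21×1.5 = 0.315
- n = [(0.891 + 0.472)/0.10]² ≈ 186 control, 372 experimental, 558 in all, against the stated 560
- power with 187 controls = Φ[(0.10×√187 − 0.891)/0.561] = Φ(0.849) = 80.2%
- attrition: 560/0.99 = 565.7, so 566, as stated

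The unpooled formula at one-sided 5% gives 195 + 390 = 585 (power 78.6% at 187/373). One-sided 2.5% gives 708 by Farrington-Manning and 744 unpooled. Neither matches 560 as closely.

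This arithmetic uses only the 30%, so it cannot show whether stroke is in it.

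**If the 30% excludes stroke**

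The documents give no 1-year stroke rate and no rate for the two composites separately. The increment is therefore an assumption, shown as a range. The top of the range, 7 points, is the highest figure in the 30-day registry summary of Section 2.3 (0.6% to 7%).

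| Points added by stroke | Composite rate | N before attrition | Power at 187/373 |
|---|---|---|---|
| 0 | 30% | 558 | 80.2% |
| 1 | 31% | 570 | 79.5% |
| 2 | 32% | 582 | 78.8% |
| 3 | 33% | 591 | 78.2% |
| 7 | 37% | 630 | 76.0% |

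**If the 30% includes stroke**, 560 stands for the declared endpoint, and only the wording of 9.1 is wrong.

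**The case against.** The weight of the text favours the three-part endpoint: four statements against one sentence in the sample-size section. That looks like a drafting omission, and the endpoint section itself is explicit. This stands as to the likely intent. It does not remove the conflict, because 9.1 says in terms what the primary endpoint is.

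A reader might infer three stronger things that the documents do not support.

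- *The trial was sized on the wrong endpoint.* The synopsis gives the same 30% and 560 beside the endpoint with stroke. Which composite the 30% describes is unresolved, and the number is not shown to be wrong.
- *The primary analysis omits stroke.* Section 9 presents the hierarchical analysis as an addition to the first-event analysis. The components of the first-event analysis are not listed again there, and nothing shows that stroke is left out of it.
- *Between 3 and 39 events would be lost.* Applying 0.6% and 7% to 560 patients gives 3.4 and 39.2, against 560×0.30 = 168 expected primary events. But these are 30-day registry rates for all strokes. Fatal strokes count as deaths, and strokes leading to admission count as readmissions. Only survived strokes without a qualifying admission, in patients with no other component event, would be lost. The 7% comes from one study with 7 events.

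It is also fair to say that a hierarchical analysis need not give every component its own tier, and that strokes will still be reported under the secondary endpoints of Section 4.2. What remains is narrower: an analysis described as assessing the primary composite should cover that composite or not be so described.

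**Conclusion.** The contradiction is real and stands in the current text. Section 9.1 defines a two-part primary endpoint against a three-part one stated four times elsewhere, and the supplementary hierarchy follows the two-part version. The practical gap is the survived stroke during the index TAVI stay. How many such events there would be cannot be derived from the documents.

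The case for correction rests on the trial needing one primary endpoint, and not on lost power. The power effect is nil if the 30% includes stroke. If it does not, power is about 1 to 2 points lower for an increment of 1 to 3 points (80.2% to 79.5% or 78.2%), and about 4 points lower at the extreme of 7. These figures depend on one-sided alpha of 5%, the Farrington-Manning method, equal rates in both arms and an assumed increment.

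**What to change.** 1. In Section 9.1, restate the primary endpoint as any of all-cause death, stroke, or hospital readmission for a cardiovascular cause within 1 year of randomization.
2. State which composite the 30% describes. The sponsor has to answer this, since the documents do not. If the 30% excludes stroke, restate the power for the three-part endpoint, or the sample size if 80% is to be kept (591 before attrition at +3 points, on the assumptions above).
3. In Section 9, add stroke as a tier between death and cardiovascular readmission, and name the last tier as cardiovascular, which its present wording does not do. Otherwise, stop describing this analysis as an assessment of the primary composite.

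The cost is a protocol wording change in two sections, made before outcome data are examined. Stroke is already a declared component and is defined in Section 8.17, so no new data collection is needed. More patients come into question only if the 30% turns out to exclude stroke and the sponsor wishes to hold power at 80%.
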